MUGA/ECHO		X	Q12W (±2 weeks) relative to randomisation (patients recruited under CSP v7.0) or first dose of study drug (patients recruited prior to CSP v7.0)						X	X ^h			8.2.5	
Concomitant medication and procedures		X	At every visit and may be conducted by phone if not tied to a clinic visit						X	X			6.5	

Visit	Pre-screening	Screening	Treatment Period						Follow-up ^a				Details in CSP section	
			Cycle 1 (28-day cycle)			Cycles 2 to 6 (28-day cycle)	Cycle 7 onwards (28-day cycle)	Treatment Discontinuation Visit	28-day Follow-up Visit ^b	Progression Follow-up ^c	Survival Follow up			
Week (Day 1 of)	NA	-4 to 0	1 to 4			5 to 24	25 onwards							
Study Day		-28 to -1	1 to 28			29 to 168	169 onwards							
Day of cycle	NA		1	8	15	22	1	1						
Visit window			±1 day			±3 days	±3 days	Within 7 days of the final dose of the last IP	±7 days	±7 days	± 7 days			
Routine safety measurements														
Adverse events		X	At every visit and may be conducted by phone if not tied to a clinic visit						X	X			8.3	
Pregnancy test (serum or urine, WOCBP only)		X	Day 1 of every cycle						X				8.2.6	
Safety laboratory assessments (clinical chemistry, haematology and urinalysis)		X	X	X	X	X	Every visit	X					8.2.1	
Coagulation		X											5.1 and 8.2.1	
Liver function tests ⁱ		X	Weekly for the first 10 weeks, then Day 1 of every subsequent cycle						X				8.2.1	
Biomarker analyses														
Blood sample for ctDNA for EGFR mutation alleles and exploratory analysis ^j			Pre-dose on Day 1 and at every subsequent visit in Cycle 1			Day 1 of Cycle 2 and then on occurrence of every RECIST 1.1 scan ^j				X (taken at progression)			8.6	

Visit	Pre-screening	Screening	Treatment Period						Follow-up ^a				Details in CSP section
			Cycle 1 (28-day cycle)			Cycles 2 to 6 (28-day cycle)	Cycle 7 onwards (28-day cycle)	Treatment Discontinuation Visit	28-day Follow-up Visit ^b	Progression Follow-up ^c	Survival Follow up		
Week (Day 1 of)	NA	-4 to 0	1 to 4			5 to 24	25 onwards						
Study Day		-28 to -1	1 to 28			29 to 168	169 onwards						
Day of cycle	NA		1	8	15	22	1	1					
Visit window			±1 day			±3 days	±3 days	Within 7 days of the final dose of the last IP	±7 days	±7 days	± 7 days		
Serum sample for circulating proteins for exploratory analysis		X	X					X					8.6
Genetic sample ^k (optional DNA element for long-term storage/future use)		X											8.7, Appendix D
HLA subtype blood sample			X										8.6
CCI													8.6
Pharmacokinetic measurements													

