PK sampling ^{n,o}			X ^o				Day 1 of Cycles 2, 3 and 6 ^o	Day 1 of Cycle 11 ^o					8.5.1

Visit	Pre-screening	Screening	Treatment Period				Follow-up ^a				Details in CSP section	
			Cycle 1 (28-day cycle)		Cycles 2 to 6 (28-day cycle)	Cycle 7 onwards (28-day cycle)	Treatment Discontinuation Visit	28-day Follow-up Visit ^b	Progression Follow-up ^c	Survival Follow up		
Week (Day 1 of)	NA	-4 to 0	1 to 4		5 to 24	25 onwards						
Study Day		-28 to -1	1 to 28		29 to 168	169 onwards						
Day of cycle	NA		1	8	15	22	1					
Visit window			±1 day		±3 days	±3 days	Within 7 days of the final dose of the last IP	±7 days	±7 days	± 7 days		
Efficacy measurements												
Tumour imaging (RECIST Version 1.1) ^p		X ^q	Q6W (±7 days) up to 24 weeks, then every Q8W (±7 days) until objective disease progression relative to randomisation (patients recruited under CSP v7.0) or the first dose of treatment (patients recruited prior to CSP v7.0)								8.1	
EORTC QLQ-C30		X	Q4W (±2 days) relative to randomisation (patients recruited under CSP v7.0) or the first dose of treatment (patients recruited prior to CSP v7.0) ^r				X ^s				8.1.2.1	
QLQ-LC13		X	Weekly (±2 days) in Cycles 1 and 2 and then Q4W (±2 days) relative to randomisation (patients recruited under CSP v7.0) or the first dose of treatment from Cycle 3 onwards (patients recruited prior to CSP v7.0) ^r				X ^s				8.1.2.1	
PGIS		X	Q8W (±2 days) relative to randomisation (patients recruited under CSP v7.0) or the first dose of treatment (patients recruited prior to CSP v7.0) ^r				X ^s				8.1.2.2	
PRO-CTCAE		X	Weekly (±2 days) in Cycles 1 and 2 and then Q4W (±2 days) relative to randomisation (patients recruited under CSP v7.0) or the first dose of treatment (patients recruited prior to CSP v7.0) from Cycle 3 onwards ^s				X ^s				8.1.2.3	

Visit	Pre-screening	Screening	Treatment Period						Follow-up ^a				Details in CSP section
			Cycle 1 (28-day cycle)			Cycles 2 to 6 (28-day cycle)	Cycle 7 onwards (28-day cycle)	Treatment Discontinuation Visit	28-day Follow-up Visit ^b	Progression Follow-up ^c	Survival Follow up		
Week (Day 1 of)	NA	-4 to 0	1 to 4			5 to 24	25 onwards						
Study Day		-28 to -1	1 to 28			29 to 168	169 onwards						
Day of cycle	NA		1	8	15	22	1	1					
Visit window			±1 day			±3 days	±3 days	Within 7 days of the final dose of the last IP	±7 days	±7 days	± 7 days		

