- e Under CSP version 7.0, only patients with central MET IHC+ and/or FISH+ status will be eligible to Screening; patients with MET status confirmed by local NGS are not eligible. Testing for MET-amplification and overexpression in tumour by FISH (centrally) and by IHC (centrally) will be performed on a tumour sample collected after progression of previous osimertinib treatment. Testing must be performed as initial prescreening with consent obtained using the Pre-screening ICF in advance of obtaining consent for the main study. Approximately **CCI** [redacted] freshly cut (within **CCI** [redacted] days) unstained sections (**CCI** [redacted] micron) from FFPE tissue blocks or FFPE blocks containing equivalent material will be required for all patients. Samples **CCI** [redacted] years old will not be accepted. New samples should only be taken specifically for Pre-screening for this study where the expected risk of an adverse event related to the procedure is <2%.
- f EGFRm status is an inclusion criterion and part of disease diagnosis; prospective central testing is not required.
- g For those patients treated on weight-based dosing regimen for savolitinib (prior to introduction of 300 mg od savolitinib dose for all new patients in CSP version 3.0), the weight captured at Screening will be used to determine the assigned dose.
- h A 28-day follow-up assessment will be required if an on-treatment assessment was abnormal at the time of discontinuation of study therapy to confirm reversibility of the abnormality.
- i Liver function tests will be performed weekly for the first 10 weeks (ie, Day 1, Day 8, Day 15 and Day 22 in Cycle 1 and Cycle 2; then Day 1 and Day 8 of Cycle 3). Where a liver function test is the only assessment, a clinic visit is not required as the test may be performed offsite. In the case of elevated liver function tests, please refer to Appendix I 3.3 for enhanced monitoring and management procedures.
- j At all visits, **CCI** [redacted] blood for plasma is required for ctDNA to measure clearance of EGFR mutation alleles and for exploratory analysis. Blood samples for ctDNA analyses requested on occurrence of every RECIST 1.1 scan should be collected on the day of the scan. If this is not possible the blood sample should be collected as close as possible to the scan within a window of ± 7 days.
- k If not taken at screening the sample may be taken at any visit until the final study visit.

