
To determine the efficacy of savolitinib (300 mg od, 300 mg bid, and 600 mg od, respectively) in combination with osimertinib in patients with EGFRm+, MET-amplified/overexpressed (FISH10+ and/or IHC90+)^a, locally advanced or metastatic NSCLC who have progressed following treatment of ≥ 2L osimertinib.
	
 • ORR by investigator assessment in accordance with RECIST 1.1. • OS

To determine the efficacy of savolitinib (300 mg od, 300 mg bid, and 600 mg od, respectively) in combination with osimertinib in patients with EGFRm+, MET-amplified/overexpressed (FISH5+ and/or IHC50+)^b, locally advanced or metastatic NSCLC who have progressed following osimertinib.
	
 • ORR (except 300 mg od), DoR, and PFS by investigator assessment in accordance with RECIST 1.1 • OS

To determine the efficacy of (1) 300 mg od, 300 mg bid and 600 mg od of savolitinib in combination with osimertinib in patients with EGFRm+ MET-amplified/overexpressed (FISH 10+ and/or IHC90+)^{a,b}; (2) 300 mg od, 300 mg bid and 600 mg od of savolitinib in combination with osimertinib. in patients with EGFRm+ MET amplified/overexpressed (FISH5+ and/or IHC50+)^b; (3) savolitinib 300 mg bid in combination with osimertinib and savolitinib 300 mg bid in combination with placebo, respectively, in patients with EGFRm+ MET-amplified/overexpressed (FISH10+ and/or IHC90+)^a following treatment with 1L osimertinib.
	
 • ORR, DoR, and PFS assessed by BICR in accordance with RECIST 1.1.

To assess the impact of savolitinib and osimertinib on disease related symptoms and HRQoL in this patient population.	
 Mean change from baseline in EORTC QLQ-C30 and QLQ-LC13.
To evaluate the pharmacokinetics of osimertinib and savolitinib in this patient population.	
 Plasma concentrations of osimertinib, savolitinib and their metabolites.
To determine the prevalence of ctDNA clearance after osimertinib and savolitinib treatment in this patient population.	
 Total clearance in EGFR mutations at 6-weeks after therapy initiation (percentage and absolute change from baseline in EGFR mutation allele frequencies).
Safety Objectives:	Endpoints:

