3.1.3 Time Windows

The date of first dose of study treatment will be considered Day 1, and the day before the first dose of study treatment will be Day -1. Relative days will be calculated as follows:

For days on or after the first dose of study treatment:

Date of assessment – Date of first dose of study treatment +1.

For days before the first dose of study treatment:

Date of assessment – Date of first dose of study treatment.

For analyses of efficacy variables for patients enrolled under CSP version 7.0, the date of randomisation will be considered Day 1, and the day before date of randomisation will be Day -1. Relative days will be calculated as follows:

For days on or after the randomisation date:

Date of assessment – Date of randomisation +1.

For days before the randomisation date:

Date of assessment – Date of randomisation.

For non-efficacy analysis, the study day is still relative to first dosing date of study treatment.

Study days will only be calculated for complete assessment dates (i.e. partial dates will have missing study day).

The time from last dose of treatment to death will be derived for complete dates as follows:

Date of death – Date of last dose of treatment

For the purpose of the statistical analysis and if not otherwise specified, all the variables (primary, secondary and exploratory variables) will be assigned to the visit/assessment timepoint in which they were collected depending on the following analysis time windows in Table 5. Where appropriate, the window for assessment days following baseline will be constructed in such a way that the upper limit of the interval falls halfway between the two timepoints.

Table 5 Time Windows

Cycle	Week	Study Day	Cycle Day	Study Day window for weekly assessments	Cycle Day window for weekly assessments	Cycle Day window for Cycle Day 1 assessments (from Cycle 2 and onwards)	Study Day window for assessments scheduled every 4 weeks [b]	Study Day window for assessments scheduled every 6 weeks	Cycle Day window for liver function tests (ALT, AST, ALP and total bilirubin)	Cycle Day window for safety laboratory assessments (other than liver function tests)
		-1	-1	-28 to -1	-1	-1	-1	-1	-1	-1
1	1	1 [a]	C1D1	1	C1D1	C1D1	1	1	C1D1	C1D1
1	2	8	C1D8	2-11	C1D2- C1D11	C1D2- C1D11	2-42	2-63	C1D8	C1D8
1	3	15	C1D15	12-18	C1D12- C1D18	C1D12- C1D18			C1D15	C1D15
1	4	22	C1D22	19-25	C1D19- C1D25	C1D19- C1D25			C1D22	C1D22
2	5	29	C2D1	26-32	C1D26- C2D4	C1D26-			C2D1	C2D1 [d]

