On treatment period includes a safety follow-up period following discontinuation of both study treatments of 28+7 days. Therefore, discontinuation visit and follow up [FUP] visit will be slotted into the appropriate analysis visit using the time windowing described in Table 5. Assessments performed after 28+7 days from final dose (i.e., outside the on-treatment period) will be labelled as 'Post follow-up' and they will be only listed.

Unscheduled visit data will be considered when assigning assessments to the analysis visit. If more than one assessment of the variable (scheduled or unscheduled) falls in the same time window but on different days, the closest to the scheduled visit day will be taken, or the earlier, in the event the values are equidistant from the nominal visit date. If several measurements are collected during the selected day, the average (for numeric values)/worst (for categorical values) of the measurements will be taken.

In summaries of extreme values as opposed to visit-based summaries, all post baseline values collected are used including those collected at unscheduled visits regardless of the value being closest to the scheduled visit date or not. For summaries at a patient level, all values should be included, regardless of whether they appear in a corresponding visit-based summary, when deriving a patient level statistic such as a maximum.

Listings will display all values contributing to a time point for a patient.

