3.2.6 Biomarker Outcome Variables

3.2.6.1 Calculation or derivation of biomarker variables

Circulating tumour deoxyribonucleic acid [ctDNA] dynamics will be evaluated as a surrogate marker of clinical efficacy.

Patients with detectable Epidermal growth factor receptor [EGFR] mutations at baseline and available data at 6 weeks will be categorised into the following groups of ctDNA status: (1) ctDNA clearance and (2) ctDNA non-clearance. Patients with undetectable EGFR mutations at baseline will be categorised as “uninformative”. Additional guidance is provided in Table 11.

Table 11 Additional guidance for ctDNA status derivation

Detectable EGFR mutation at baseline	Positive pre-dose result for L858R or exon 19 deletion
Evaluable at 6-weeks	1. Detectable EGFR mutation at baseline AND 2. Evaluable result at 6-weeks ^a
ctDNA clearance	1. Evaluable at 6-weeks AND 2. Negative result at 6-weeks
ctDNA non-clearance	1. Evaluable at 6-weeks AND 2. Positive result at 6-weeks

Not evaluable at 6-weeks	Data otherwise not considered evaluable at 6-weeks
Uninformative assessment at baseline	Negative pre-dose result for L858R or exon 19 deletion
Evaluable data at 6-weeks	1. Uninformative assessment AND 2. Positive or negative post-dose result at 6-weeks
Not evaluable data at 6-weeks	1. Uninformative assessment AND 2. Data otherwise not considered at 6-weeks
Missing baseline assessment	No pre-dose result for L858R or exon 19 deletion
Evaluable data at 6-weeks	1. Missing baseline assessment AND 2. Positive or negative result at 6-weeks
Not evaluable at 6-weeks	1. Missing baseline assessment AND 2. Data otherwise not considered evaluable at 6- weeks

a: Evaluable result at 6-weeks = baseline detectable EGFR mutation for L858R AND positive/negative L858R result at 6-weeks, OR, baseline detectable EGFR mutation for exon 19 deletion AND positive/negative exon 19 deletion result at 6-weeks.

Note: Rare cases where a patient is reported to have both L858R and exon 19 deletion mutations at baseline and/or follow-up and the rules above still applicable to declare ctDNA clearance of at least one mutation. Patients with a single mutation at baseline, but the alternative mutation is observed at 6-weeks are considered not-evaluable at 6-weeks, as described in 'a' above.

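### The SAP sets no day range for the 6-week ctDNA result, so the default window can score a patient with no 6-week sample on an earlier one, and the dual-mutation note contradicts total clearance

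*SAP*

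**What the plan says.** - **Endpoint** (SAP Section 1, Table 1; the same in Protocol Section 3): "Total clearance in EGFR mutations at 6-weeks after therapy initiation".
- **Sampling** (Protocol 1.1, Table 1): blood for ctDNA is drawn "Pre-dose on Day 1 and at every subsequent visit in Cycle 1", then "Day 1 of Cycle 2 and then on occurrence of every RECIST 1.1 scan". Scans are "Q6W (±7 days) up to 24 weeks". If blood cannot be drawn on the scan day, it is drawn "as close as possible to the scan within a window of ± 7 days".
- **Classification** (SAP 3.2.6.1, Table 11): patients with a mutation detected at baseline are cleared, not cleared, or not evaluable at 6 weeks. No days are attached to 6 weeks.
- **Default windows** (SAP 3.1.3): unless something else is specified, "all the variables (primary, secondary and exploratory variables) will be assigned to the visit/assessment timepoint in which they were collected", by the windows of Table 5. If several samples fall in one window, "the closest to the scheduled visit day will be taken", and the earlier one if they are equally close. No Table 5 column is named for ctDNA. The first post-baseline window for 6-weekly assessments is Day 2 to 63. In the weekly column the Week 6 row is Day 33 to 39 and the Week 7 row is Day 40 to 46.
- **Two mutations** (note to Table 11): in the rare patient with both L858R and exon 19 deletion, "the rules above still applicable to declare ctDNA clearance of at least one mutation".
- **Reporting** (SAP 4.2.2.8.1): number and percentage by clearance status, and descriptive statistics for the change in allele frequency at Week 6. There is no test.

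**The concern.** From Day 29 on, ctDNA follows the scans, so the 6-weekly column is the one a programmer is likely to choose. Its first window also holds the Day 8, 15, 22 and 29 samples. For a patient who never gave a 6-week sample, the closest-sample rule then supplies an earlier one. That patient enters the denominator and is called cleared or not cleared on one to four weeks of treatment, and the Week 6 percentage change is affected in the same way. Table 11 has a not-evaluable category for exactly this patient. SAP 2.3 (Table 4, item 7.05) lists missing 6-week ctDNA as an important protocol deviation, so one patient could be listed as lacking the result and also counted as having it.

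The dual-mutation note is a separate matter. A patient with one negative and one positive result meets the Table 11 definitions of both clearance and non-clearance, and the note settles the case as clearance. The endpoint is total clearance.

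**Working it through.** **1. Reproduce Table 5.** SAP 3.1.3 puts the upper limit of each window halfway between neighbouring timepoints. With 6-weekly targets of Day 42, 84, 126 and 168:
- (42 + 84)/2 = 63, (84 + 126)/2 = 105 and (126 + 168)/2 = 147.
- The windows are Day 2–63, 64–105 and 106–147, as in Table 5. Targets of 43, 85 and 127 would give 2–64 and 65–106, which do not match, so the implied target is Day 42.
- Weekly targets of 29, 36, 43 and 50 have midpoints 32.5, 39.5 and 46.5, which give Day 33–39 and 40–46, also as printed.

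**2. Place the planned samples.** Days 8, 15, 22, 29 and 42/43 all lie in Day 2–63.

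**3. Apply the closest-sample rule in that window.**

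| Samples available | Sample used |
|---|---|
| 8, 15, 22, 29, 43 | 43 |
| 8, 15, 22, 29 | 29 |
| 8, 15, 22 | 22 |
| 8 | 8 |

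An on-time sample always wins. An early sample is used when the 6-week sample is absent.

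**4. Very late samples.** The first scan may fall on Day 43 ± 7 = Day 36–50, and the blood a further ± 7 days, so Day 29–57.
- Target Day 42, Cycle 2 Day 1 sample on Day 29: its distance is 13. A 6-week sample on Day 55 is also 13 away, and the tie goes to the earlier one. Day 29 therefore replaces anything from Day 55.
- Target Day 43: the distances tie at 14, so only a Day 57 sample is replaced.
- Cycle 2 Day 1 sample on Day 32 (the visit allows ± 3 days): it replaces samples from Day 52 (target 42) or Day 54 (target 43).

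**5. Windows from the ctDNA schedule itself.** Apply the same halfway rule to Days 29, 42 and 84. (29 + 42)/2 = 35.5 and (42 + 84)/2 = 63, so the 6-week window is Day 36–63. With targets 43 and 85 it is Day 37–64. Both exclude the nominal Day 8 to 29 samples and keep Day 42/43.

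**6. Size, on assumed inputs only.** Let m be the share of patients counted as evaluable who were read on an early sample, and d the difference in clearance between their early samples and true 6-week samples. The reported prevalence shifts by m × d.
- m = 5%, d = 10 points: 0.5 points.
- m = 20%, d = 30 points: 6 points.
- m = 20%, d = 50 points: 10 points.

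For the dual-mutation note the inflation cannot exceed the share of dual-mutation patients: at most 1 to 5 points if that share is 1% to 5% (assumed).

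**The case against.** The strongest reply is that Day 2–63 need not be the window at all. The SAP assigns ctDNA to no column, and its halfway rule, used where appropriate, gives about Day 36–63 on the ctDNA schedule. SAP 4.2.2.8.1 also asks for individual changes at all post-baseline timepoints, which a single Day 2–63 bin could not show. This stands as a sensible reading. It does not remove the point, because the SAP does not tell the programmer to take it and the readings give different denominators.

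A reader might infer more than the documents support:
- **That every patient's Week 6 result is at risk.** It is not. An on-time sample is always selected (step 3).
- **That the weekly column misplaces the 6-week sample by calling it Week 7.** This is mostly a label. Table 5 starts at Week 1 on Day 1, so its Week 7 row (Day 43) is six completed weeks. It becomes an error only if the program picks the row labelled Week 6.
- **That patients without a 6-week sample are mainly early stoppers, unevenly spread over regimens.** Nothing in the documents shows this. Under Protocol Table 1 (footnote on tumour assessments after discontinuation), patients who stop drug without progression continue scans, with ctDNA samples at the same time points.

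On the dual-mutation note, the fair reply is that such cases are rare by the SAP's own account. That limits the effect but does not reconcile the note with the endpoint.

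**Conclusion.** Two defects stand, both modest. First, the 6-week ctDNA result has no day range. Under the 6-weekly default, a patient with a missing 6-week sample is reported on an earlier one, and a very late 6-week sample can lose to the Cycle 2 Day 1 sample. Second, the dual-mutation note contradicts total clearance and can only raise the reported rate.

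The documents give no missing-sample rate, no clearance rate at any time and no dual-mutation frequency. The ranges in step 6 therefore show scale and are not estimates. The direction of the window effect is not known either: it depends on whether early samples clear more or less often than 6-week samples. The conclusion on the window rests on the 6-weekly column being used, which the SAP neither states nor rules out. The endpoint is secondary and descriptive, so no error rate or power is involved and the primary ORR is unaffected.

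**What to change.** In SAP 3.2.6.1:
1. Define the 6-week ctDNA result as the sample linked to the first scheduled scan, target Day 42/43, for example Day 36–63 by the SAP's own halfway rule.
2. Also accept an earlier sample that was explicitly drawn for that scan within the protocol tolerance, since a compliant one can fall as early as Day 29. Never use the Cycle 1 or Cycle 2 Day 1 visit samples.
3. Classify patients with no such sample as not evaluable at 6 weeks, and apply the same definition to the Week 6 change in allele frequency.
4. Change the Table 11 note so that clearance requires every mutation detected at baseline to be negative at 6 weeks.

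The cost is SAP wording and programming, with no new data collection. The downside is slightly fewer evaluable patients and a slightly lower clearance rate where both mutations were present at baseline.

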7.1.3 Follow-up of patients post discontinuation of study intervention

As a minimum, telephone contact should be made with the patient 28 days following the discontinuation of both IPs to collect new AEs and follow up on any ongoing AEs and concomitant medications (including any subsequent cancer therapy, if appropriate). Refer to Section 8.3.3 for full details on AE recordings during follow-up.

Patients who have discontinued study intervention prior to RECIST 1.1 defined radiological progression will be followed up with tumour assessments as indicated in the SoA until RECIST 1.1-defined PD or death regardless of whether or not the patient started a subsequent anti-cancer therapy, unless they have withdrawn all consent to study related assessments.

All patients will be followed for survival until the end of the study.

Patients who decline to return to the site for evaluations should be contacted by telephone as indicated in the SoA as an alternative.

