Early Phase Oncology Statistical Analysis Plan

Study Code D5084C00007

Edition Number 7.0

Date 03/07/2024

2	6	36	C2D8	33-39	C2D5-C2D11	C2D25			C2D8	
2	7	43	C2D15	40-46	C2D12-C2D18	C2D26-C3D25	43-70	64-105	C2D15	C3D1 [d]
2	8	50	C2D22	47-53	C2D19-C2D25				C2D22	
3	9	57	C3D1	54-60	C2D26-C3D4				C3D1	
3	10	64	C3D8	61-67	C3D5-C3D11				C3D8 [e]	
3	11	71	C3D15	68-74	C3D12-C3D18				C4D1 [d]	
3	12	78	C3D22	75-81	C3D19-C3D25				C4D1 [d]	
4	13	85	C4D1	82-88	C3D26-C4D4		71-98	99-126		
4	14	92	C4D8	89-95	C4D5-C4D11					
4	15	99	C4D15	96-102	C4D12-C4D18	C3D26-C4D25				

4	16	106	C4D22	103-109	C4D19-C4D25		106-147		
5	17	113	C5D1	110-116	C4D26-C5D4	C4D26-C5D25		C5D1 [d]	C5D1 [d]
5	18	120	C5D8	117-123	C5D5-C5D11				
5	19	127	C5D15	124-130	C5D12-C5D18				
5	20	134	C5D22	131-137	C5D19-C5D25				
				Etc. for Cycles 6 and above					After Week 24, tumour assessments will be every 8 weeks [c]

[a] Measurements collected before the first dose of study treatment/randomisation on Day 1 are pre-dose values and measurements collected after first dose of study treatment/randomisation on Day 1 are post-baseline values. For ePRO questionnaires, the baseline is defined as the non-missing assessment collected at Day 1, as it is assumed it is taken prior to start of the study treatment. If an assessment is missing at Day 1, the prior non-missing assessment will be used as baseline.

[b] The Week 24 window would start approximately halfway through a 6-week period and end halfway into an 8-week period, i.e. Day 196. Week 32 window will be Day 197-252, etc.

[c] For assessments occurring every 12 weeks, the same schedule should be used, i.e. for the first assessment on Day 84 the window will be Day 1-126, for the second assessment on Day 168 the window will be Day 127-210, etc.

[d] The target day will be the study day at CXD1

[e] The target day will be the study day at C3D8

The treatment discontinuation visit should occur within 7 days of the final dose of the last study treatment. For the 28-day follow-up visit a 7-day window is allowed, i.e., it should occur 21-35 days following discontinuation of both study treatments.

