3.2.1.1.5 Progression Free Survival [PFS]

PFS is defined as the time from first dose randomisation (patients recruited under CSP version 7.0) or start of treatment (patients recruited prior to CSP version 7.0) until the date of objective disease progression or death (by any cause in the absence of progression) regardless of whether the patient withdraws from study therapy or receives another anti-cancer therapy prior to progression (i.e. date of PFS event or censoring – date of first dose + 1). Patients who have not progressed or died at the time of analysis will be censored at the time of the latest date of assessment from their last evaluable RECIST assessment. However, if the patient progresses or dies after 2 or more missed visits, the patient will be censored at the time of the latest evaluable RECIST 1.1 assessment prior to the two missed visits.

If the two missed visits are immediately after the baseline scan then the definition of two missed visits should be calculated as 2*(the protocolled time between scans) + the protocol allowed visit window (since there is no need to account for an early initial visit in this case), otherwise this should be calculated as 2*(the protocolled time between scans + the protocol allowed visit window). Given the scheduled visit assessment scheme (i.e. six-weekly for the first 24 weeks then eight-weekly thereafter) the definition of 2 missed visits will change as follows:

Last evaluable RECIST assessment before event	Length of time of 2 missed visits
Baseline	2 x 6 weeks + 1 week for late assessment = 13 weeks
RECIST visit 1	2 x (6 weeks + 1 week) = 14 weeks
RECIST visit 2	2 x (6 weeks + 1 week) = 14 weeks
RECIST visit 3	(6 weeks + 1 week) + (8 weeks + 1 week) = 16 weeks
RECIST visit 4	2 x (8 weeks + 1 week) = 18 weeks
RECIST visit 5 etc	2 x (8 weeks + 1 week) = 18 weeks

If the patient has no evaluable visits or does not have baseline data, they will be censored at Day 1 unless they die within 2 visits of baseline (12 weeks plus 1 week allowing for a late assessment within the visit window).

The PFS time will always be derived based on scan/assessment dates, not visit dates.

RECIST assessments/scans contributing towards a particular visit may be performed on different dates. The following rules will be applied:

- For investigational assessments, the date of progression will be determined based on the **earliest** of the dates of the component that triggered the progression

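### SAP 3.1.3 makes tumour scans taken more than 35 days after the last dose listing-only, which takes observed values out of the Week 12 and over-time tumour-size summaries

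*SAP*

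**What the plan says.** SAP 3.1.3 (Time Windows) sets a default scope: "if not otherwise specified, all the variables (primary, secondary and exploratory variables) will be assigned to the visit/assessment timepoint" according to Table 5. That table has a column for 6-weekly assessments and the entry "After Week 24, tumour assessments will be every 8 weeks", so tumour scans were in view when it was written.

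The section then defines the period: "On treatment period includes a safety follow-up period following discontinuation of both study treatments of 28+7 days". What falls later is dealt with in one sentence: "Assessments performed after 28+7 days from final dose (i.e., outside the on-treatment period) will be labelled as" Post follow-up, "and they will be only listed". It makes no exception for scans. The same section does say that summaries of extreme values use all post-baseline values and that patient-level summaries include all values.

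Scanning does not stop with treatment. Under protocol 7.1.3, patients who stop before progression "will be followed up with tumour assessments as indicated in the SoA until RECIST 1.1-defined PD or death". SAP 3.2.1.1.1 says the same.

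For tumour size, SAP 3.2.1.1.4 says that target-lesion data available for a visit are to be used in the tables and figures. It imputes Week 12 only when no Week 12 value was observed. SAP 4.2.2.13.1 summarises percentage change at Week 12 and over time, with a Week 12 waterfall plot.

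**The concern.** The 35-day limit suits adverse events, laboratory tests and ECGs, where the aim is to describe what happens under exposure. It does not suit tumour measurements, which the protocol deliberately collects after treatment stops. Applied as written, it takes a measured Week 12 tumour size out of the summary and leaves the gap to the imputation rules.

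Patients who stop both drugs within about seven weeks without progression have often stopped for toxicity and are not a random subset. Their tumours may regrow once treatment ends. Replacing the observed value with one projected from on-treatment scans, or excluding the patient as missing completely at random, could therefore shift the Week 12 distribution and the waterfall plot. Two programmers could each follow the SAP, one relying on 3.1.3 and the other on 3.2.1.1.4, and produce different tables.

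**Working it through.** **1. The limit.** 28 + 7 = 35 days. This agrees with the 35-day follow-up period in SAP 4.2.3.2 (adverse events).

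**2. Scan calendar.** Scans at Weeks 6, 12, 18 and 24, then every 8 weeks, fall on Days 43, 85, 127, 169, 225 and so on (day = 7 × week + 1). The intervals of 42 and 56 days both exceed 35.

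**3. Week 12.** With last dose of both drugs on Day L, the Day 85 scan is listing-only if 85 − L > 35, that is, L ≤ 49. For a scan at either end of the ±7-day window, the limits are 78 − 36 = Day 42 and 92 − 36 = Day 56. All these scan days lie inside the Table 5 window of Days 64 to 105, so without the rule they would count as Week 12 values.

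**4. First off-treatment scan.** Let the last dose fall d whole days after the previous scan, spread evenly (an assumption). The next scan is beyond the limit when interval − d > 35.

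| Phase | Next scan on schedule | 7 days early | 7 days late |
|---|---|---|---|
| 6-weekly | 7/42 = 17% | 0/35 = 0% | 14/42 = 33% |
| 8-weekly | 21/56 = 38% | 14/49 = 29% | 28/56 = 50% |

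On the nominal schedule a second off-treatment scan comes at least 42 + 1 = 43 days after the last dose, so every second or later one is beyond the limit.

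**5. What replaces the observed value.** For Week 12, step (a) of SAP 3.2.1.1.4 fits a line through the patient's other measurements. If later scans are also listing-only, these are baseline and Week 6. A line through two points carries the Week 6 change forward by (85 − 1)/(43 − 1) = 2 times if baseline is at Day 1, or by (84 + 28)/(42 + 28) = 1.6 times if baseline is 28 days earlier, the protocol 8.1.1 limit. A 30% shrinkage at Week 6 would then enter as 48% to 60% at Week 12, whatever the real scan showed. If L ≤ 7, the Day 43 scan is listing-only too (43 − 7 = 36). Step (c) then excludes the patient if there is no evidence of progression. The over-time summaries are not imputed, so there the value simply disappears.

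**6. Which outputs are exposed.**

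| Output | Governing rule in the SAP | Affected? |
|---|---|---|
| ORR, best response | 3.2.1.1.2: data to progression or last evaluable scan; responses after subsequent anti-cancer therapy not counted | No |
| PFS | 3.2.1.1.5: "regardless of whether the patient withdraws from study therapy or receives another anti-cancer therapy prior to progression"; dated by scan, not by visit | No |
| DoR | 3.2.1.1.3: end date taken from PFS | No |
| Best percentage change | 3.1.3: extreme-value and patient-level rules use all values | No |
| Tumour size at Week 12 (including waterfall plot) and over time | 3.2.1.1.4 and 4.2.2.13.1: depends on visit windows | Yes |

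**The case against.** The best defence is that the sentence was meant for safety data. The 35 days are introduced as a safety follow-up period, next to text on slotting the discontinuation and 28-day visits, and 4.2.3.2 repeats the limit for adverse events. The section's scope is a default that yields to specific rules. SAP 3.2.1.1.4 is such a rule, and it imputes only when nothing was observed at Week 12. The clock also starts only when both drugs have stopped, and patients may continue on one, which limits the number affected.

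Most of this stands. It disposes of a stronger reading that a reader might draw from the reference to primary and secondary variables: that off-treatment scans drop out of ORR, DoR and PFS, so that confirmed responses are lost and progressions censored. The documents do not support that. Each of those endpoints is specified otherwise, and SAP 4.2.2.4 tabulates patients who stopped treatment before progressing, which presupposes that off-treatment progressions count.

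The defence does not fully cover tumour size by visit. SAP 3.2.1.1.4 speaks of data for the visit and of the window used to select Week 12 data. That sends the reader back to 3.1.3, where a late off-treatment scan is labelled as post follow-up rather than as a visit. Unlike PFS, this analysis has no statement that it runs regardless of treatment status.

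**Conclusion.** The point holds for visit-based tumour-size summaries only. There, 3.1.3 and 3.2.1.1.4 give conflicting instructions, and following 3.1.3 gives the worse result: a measured value is discarded and then imputed, excluded or dropped. The exposure is the Day 49 threshold for Week 12, and 17% (0% to 33%) or 38% (29% to 50%) of first off-treatment scans by phase. These shares rest on evenly spread last doses. The documents do not say how many patients stop both drugs before progression, so the net effect on the summaries cannot be sized, nor its direction fixed.

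Tumour-size change is exploratory, and SAP section 6 lists it as an addition to the protocol. No loss of responders in the primary ORR and no bias in PFS or DoR should be inferred. Sample size, power and alpha are unaffected.

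**What to change.** In SAP 3.1.3, limit the listing-only sentence to laboratory, vital sign, ECG and other safety assessments, and add:

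*RECIST assessments, including target-lesion tumour size by visit, are assigned to Table 5 windows and summarised irrespective of time since last dose; ORR, DoR and PFS follow sections 3.2.1.1.2, 3.2.1.1.3 and 3.2.1.1.5, including their subsequent-therapy and missed-visit rules.*

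The last clause is needed. A blanket instruction to use every scan would contradict the exclusion of responses after subsequent anti-cancer therapy and the PFS censoring after two missed visits. The cost is two sentences in the SAP and a check that the tumour-size programs apply no 35-day filter. It needs no new data and no protocol change.
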